## Intraoperative

Date of surgery (YYYY-MM-DD): 20__ - __ - __			
Name of surgery: _____			
Anesthesia techniques and drug details			
 GA;  Combined GA-epidural;  Other: _____			
Anesthesia induction (HH:MM): __: __			
Extubation (HH:MM): __: __			
Duration of anesthesia (from anesthesia induction to extubation): ___ mins			
Skin incision (HH:MM): __: __			
Skin closure (HH:MM): __: __			
Duration of surgery (from skin incision to closure): ___ mins			
Anesthesia induction			
Check if yes	Drug	Dose	Route
	Lidocaine		
	Propofol		
	Sufentanil		
	Rocuronium		
	Fentanyl		
	Succinylcholine		
	Midazolam		
	Morphine		
	Etomidate		
	Other:		
	Other:		
Anesthesia maintenance			
Check if yes	Drug	Dose	Route
	Propofol		infusion
	Remifentanil		infusion
	Sufentanil		
	Sevoflurane		
	Dexmedetomidine		
	Fentanyl		
	Morphine		
	Rocuronium		
	Vecuronium		
	Cisatracurium		
	Other:		
	Other:		

Epidural drugs			
Check if yes	Drug	Dose	Route
	Lidocaine		
	Ropivacaine		
	Bupivacaine		
	Fentanyl		
	Other:		
	Other:		
Other drugs			
Check if yes	Drug	Dose	Route
	Dexamethasone		
	Methylprednisolone		
	Hydrocortisone		
	Ondansetron		
	Tropisetron		
	Atropine		
	Glycopyrrolate		
	Scopolamine		
	Neostigmine		
	Penhyclidine		
	Other:		
	Other:		
Intraoperative inputs			
Check if yes	Name	Total volume (mL)	
	0.9% NS		
	LR		
	Plasmalyte		
	5% Albumin		
	Colloid:		
	PRBC		
	FFP		
	Platelet		
	Cellsaver		
	Other:		
Intraoperative outputs			

Check if yes	Name	Total volume (mL)
	Estimated blood loss	
	Urine output	
	Other:	
	Other:	
Lowest hemoglobin (Hb) level during surgery if available __. __ (g/L)		
Highest lactate level during surgery if available __. __ (mmol/L)		
Procedure converted to open surgery: Yes  ; No  ; Reason: _____		
Procedure aborted: Yes  ; No  ; Reason: _____		

### Postoperative

Extubation at the end of surgery:  Yes;  No			
PACU admission:  Yes;  No			
Date (YYYY-MM-DD): 20__-__-__	Time in (hh: mm): __: __	Time out (hh: mm): __: __	PACU length: ___ mins
ICU admission:  Yes;  No			
Date (YYYY-MM-DD) in: 20__-__-__	Time in (hh: mm): __: __	Date (YYYY-MM-DD) out: 20__-__-__	ICU days: __ days
Details of extubation if not extubated at the end of surgery in the Operating Room			
Location:  PACU;  ICU			
Duration from the end of surgery to extubation: __ hours, or, __ days			

## Delirium Assessment (performed at both PACU and floor/ICU)

Date	Time	RASS -5 to +4	Feature 1: Acute Onset or Fluctuating Course	Feature 2: Inattention	Feature 3: Altered Level of Consciousness	Feature 4: Disorganized Thinking	Delirium Diagnosis
PACU	30 mins after extubation to Discharge		 Yes  No				
POD 1	8:00-10:00		 Yes  No				
	16:00-18:00		 Yes  No				
POD 2	8:00-10:00		 Yes  No				
	16:00-18:00		 Yes  No				
POD 3	8:00-10:00		 Yes  No				
	16:00-18:00		 Yes  No				
POD 4	8:00-10:00		 Yes  No				
	16:00-18:00		 Yes  No				
POD 5	8:00-10:00		 Yes  No				
	16:00-18:00		 Yes  No				

**Diagnosis of Emergence Delirium:**  Yes  No

**Diagnosis of POD:**  Yes  No

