## 7.3 Postoperative data

- 1) PACU Delirium: Occurrence of delirium in PACU will be assessed using the CAM-ICU 30 mins after extubation and before PACU discharge.
- 2) Postoperative Delirium (POD): POD will be assessed twice daily (8:00-10:00 am, and 18:00-20:00 pm) for 5 days from postoperative day 1 to 5 or until the patient is discharged home if the patient stays in hospital < 5 days. CAM is used for delirium assessment if the patient is on the floor; otherwise, CAM-ICU is used if the patient is in the ICU. Investigators for POD assessment will be trained by a psychiatrist to use CAM and CAM-ICU before the trial is commenced.
- 3) Non-delirium Complications: Any complications occurred within the first 30 days after surgery (for example: cardiac events, cerebrovascular events, renal injury, GI complications, infections, etc.) will be documented. Patients will be assessed via phone call if they are discharged before day 30 after surgery.
- 4) Subjective Pain Score: It will be assessed at PACU and 24 hours after surgery using the Numeric Rating Scale (NRS) (an 11-point scale where 0 indicates no pain and 10 indicates the worst pain).
- 5) Subjective Sleep Quality: It will be assessed at 8:00 am during the first postoperative day using the NRS (an 11-point scale where 0 indicates the best possible sleep and 10 indicates the worst possible sleep).
- 6) Length of Hospital Stay: The readiness for discharge will be used as the last day of hospitalization.
- 7) All-cause 30-day Mortality: Patients or family members will be called for assessment.
- 8) Adverse Events: If an adverse event occurs during patient hospitalization, it will be followed up until its disappearance or therapy ends.

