## 8. Outcome

### 8.1 Primary outcome

Incidence of postoperative delirium during the first 5 days after surgery.

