### Supplemental remark 3.

## The Confusion Assessment Method (CAM) Instrument for patients NOT in ICU (A Chinese version is needed.)

Aspects	Assessments	Conclusion									
		Day-1		Day-2		Day-3		Day-4		Day-5	
		AM	PM								
1. [Acute Onset]	Is there evidence of an acute change in mental status from the patient's baseline?	 Yes  No									
2A. [Inattention]	Did the patient have difficulty focusing attention, for example, being easily distractible, or having difficulty keeping track of what was being said?	 Yes  No									
2B. (If present or abnormal)	Did this behavior fluctuate during the interview, that is, tend to come and go or increase and decrease in severity?	 Yes  No									
3. [Disorganized thinking]	Was the patient's thinking disorganized or incoherent, such as rambling or irrelevant conversation, unclear or illogical flow of ideas, or unpredictable switching from subject to subject?	 Yes  No									
4. [Altered level of consciousness]	Overall, how would you rate this patient's level of consciousness? (Alert [normal]; Vigilant [hyperalert, overly sensitive to environmental stimuli, startled very easily], Lethargic [drowsy, easily aroused]; Stupor [difficult to arouse]; Coma; [unarousable]; Uncertain)	 Yes  No									
5. [Disorientation]	Was the patient disoriented at any time during the interview, such as thinking that he or she was somewhere other than the hospital, using the wrong bed, or misjudging the time of day?	 Yes  No									

6. [Memory impairment]	Did the patient demonstrate any memory problems during the interview, such as inability to remember events in the hospital or difficulty remembering instructions?	 Yes  No									
7. [Perceptual disturbances]	Did the patient have any evidence of perceptual disturbances, for example, hallucinations, illusions or misinterpretations (such as thinking something was moving when it was not)?	 Yes  No									

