## The Confusion Assessment Method (CAM) Diagnostic Algorithm

Features	Description & Assessments	Conclusion									
		Day-1		Day-2		Day-3		Day-4		Day-5	
		AM	PM	AM	PM	AM	AM	PM	AM	PM	AM
Feature 1: Acute Onset and Fluctuating Course	This feature is usually obtained from a family member or nurse and is shown by positive responses to the following questions: Is there evidence of an acute change in mental status from the patient's baseline? Did the (abnormal) behavior fluctuate during the day, that is, tend to come and go, or increase and decrease in severity?	 Yes  No									
Feature 2: Inattention	This feature is shown by a positive response to the following question: Did the patient have difficulty focusing attention, for example, being easily distractible, or having difficulty keeping track of what was being said?	 Yes  No									
Feature 3: Disorganized thinking	This feature is shown by a positive response to the following question: Was the patient's thinking disorganized or incoherent, such as rambling or irrelevant conversation, unclear or illogical flow of ideas, or unpredictable switching from subject to subject?	 Yes  No									
Feature 4: Altered Level of consciousness	This feature is shown by any answer other than "alert" to the following question: Overall, how would you rate this patient's level of consciousness? (alert [normal]), vigilant [hyperalert], lethargic [drowsy, easily aroused], stupor [difficult to arouse], or coma [unarousable])	 Yes  No									

Is the patient delirious?	The diagnosis of delirium by CAM requires the presence of features 1 and 2 and either 3 or 4.	 Yes  No									
----------------------------------	--	---	---	---	---	---	---	---	---	---	---

Inouye SK, van Dyck CH, Alessi CA, Balkin S, Siegel AP, Horwitz RI. Clarifying confusion: the confusion assessment method. A new method for detection of delirium. Ann Intern Med. 1990;113(12):941-8.

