## Patient RASS Scores

Location/date	PACU	POD-1		POD-2		POD-3		POD-4		POD-5	
Time		AM	PM								
Score											

**If the RASS score is > -4 (-3 through +4), delirium is assessed using the CAM-ICU Worksheet  
CAM-ICU Worksheet**

Features	Score	Check here if present		
Feature 1: Acute Onset or Fluctuating Course				

Is the patient different than his/her baseline mental status? OR Has the patient had any fluctuation in mental status in the past 24 hours as evidenced by fluctuation on a sedation/level of consciousness scale (i.e., RASS/SAS), GCS, or previous delirium assessment?
	Either question Yes			
Feature 2: Inattention				

Letters Attention Test (See training manual for alternate Pictures) Directions: Say to the patient, “I am going to read you a series of 10 letters. Whenever you hear the letter ‘A,’ indicate by squeezing my hand.” Read letters from the following letter list in a normal tone 3 seconds apart. S A V E A H A A R T or C A S A B L A N C A or A B A D B A D A A Y Errors are counted when patient fails to squeeze on the letter “A” and when the patient squeezes on any letter other than “A.”
	Number of Errors >2			
Feature 3: Altered Level of Consciousness				
Present if the Actual RASS score is anything other than alert and calm (zero)	RASS anything other than zero			
Feature 4: Disorganized Thinking				

Yes/No Questions (Use group A or group B to test, if necessary, group A and B can be used interchangeably)
 
Group A:
 
 
1. Will a stone float on water?
 
2. Are there fish in the sea?
 
3. Does one pound weigh more than two pounds?
 
4. Can you use a hammer to pound a nail?
 
 
Group B:
 
 
1. Will a leaf float on water?
 
2. Are there elephants in the sea?
 
3. Does two pounds weigh more than one pound?
 
4. Can you use a hammer to saw wood?
 
			Combined number of errors >1	

Errors are counted when the patient incorrectly answers a question.			

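### The shared CRF delirium grid prints the either/or wording of Feature 1 for floor patients, whose CAM requires both limbs, and no rule says which form decides the primary outcome

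*Combined protocol and SAP*

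**What the plan says.** The primary outcome (8.1) is "Incidence of postoperative delirium during the first 5 days after surgery". Section 7.3, item 2, fixes the instrument by location: "CAM is used for delirium assessment if the patient is on the floor; otherwise, CAM-ICU is used if the patient is in the ICU".

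The two instruments appear as appendices. Supplemental remark 3 is the CAM, titled "Instrument for patients NOT in ICU". Its diagnostic algorithm calls Feature 1 "Acute Onset and Fluctuating Course" and lists two questions, one on acute change and one on fluctuation, to be answered positively. Supplemental remark 4 is the CAM-ICU worksheet for PACU and ICU. Its Feature 1 is met when "Either question Yes".

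The CRF collects all delirium assessments on one page, headed "Delirium Assessment (performed at both PACU and floor/ICU". The Feature 1 column is headed "Acute Onset or Fluctuating Course" and covers the PACU row and all day 1 to 5 rows. The page has a diagnosis column for each visit and, below the grid, a yes/no box for "Diagnosis of POD".

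**The concern.** For a floor patient the protocol provides two places to record a delirium diagnosis: the CAM algorithm sheet, which has its own yes/no line at each assessment, and the CRF grid. They word Feature 1 differently, and Feature 1 is necessary for a diagnosis under both instruments. The page that carries the overall outcome box has the wording of the instrument that floor patients are not assigned.

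At stake is whether the primary outcome has one case definition. Sections 8.1 and 13.5 name the outcome and the test, but give no rule for deriving a patient's status from the assessments. If two forms can disagree and no rule ranks them, the number of events depends on which form is entered in the database.

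**Working it through.** **1. The forms side by side**

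| Form | Used for | Feature 1 |
|---|---|---|
| CAM algorithm (Supplemental remark 3) | patients outside the ICU | acute change AND fluctuation |
| CAM-ICU worksheet (Supplemental remark 4) | PACU and ICU | acute change OR fluctuation |
| CRF delirium grid | PACU, floor and ICU | heading says OR, for all rows |

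Both instruments combine features in the same way: 1 and 2 and (3 or 4). The grid prints headings but no combining rule, so the next step applies this common rule to the grid's Feature 1 heading.

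**2. Which symptom patterns are classified differently**

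Let A = acute change, F = fluctuation, I = inattention, D = disorganized thinking, C = altered consciousness.

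- CAM sheet: (A and F) and I and (D or C)
- Grid heading: (A or F) and I and (D or C)

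The five symptoms give 2^5 = 32 patterns. The rules differ when exactly one of A and F is present (2 ways), I is present (1 way), and D, C or both are present (3 ways): 2 × 1 × 3 = 6 patterns. All six are positive under the grid heading and negative on the CAM sheet. For example, a floor patient who is newly drowsy and inattentive, without fluctuation, has A, I and C but not F.

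Six of 32 counts patterns. It does not estimate how many patients are affected.

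**3. The plan's own sample size**

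Inputs from section 4.2: control rate p1 = 0.14; reduction by one third, so p2 = 0.14 × 2/3 = 0.0933; two-sided alpha 0.05; power 80%. Allocation is 1:1 (5.1). With mean rate p̄ = 0.1167 and d = 0.0467:

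n = [1.960 √(2p̄(1−p̄)) + 0.8416 √(p1(1−p1) + p2(1−p2))]² / d²
= [1.960 × 0.4540 + 0.8416 × 0.4528]² / 0.0467² = 742 per group after rounding up.

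This matches the plan and is not in dispute.

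**4. What the discrepancy could do to power**

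The documents do not give the share of floor patients with only one limb, so every row is an assumption. Power at n = 742 per group is Φ((d − 1.960·SE0)/SE1), where SE0 is the pooled and SE1 the unpooled standard error.

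| Assumption | Rates | RR | Power |
|---|---|---|---|
| Planning values | 14.0% vs 9.33% | 0.667 | 80.0% |
| (a) OR adds noise, p + q(1−p), q = 1% | 14.86% vs 10.24% | 0.689 | 76.7% |
| (a) q = 2% | 15.72% vs 11.15% | 0.709 | 73.4% |
| (a) q = 4% | 17.44% vs 12.96% | 0.743 | 67.2% |
| (b) OR adds true cases with the same one-third reduction, p(1+g), g = 10% | 15.4% vs 10.27% | 0.667 | 84.1% |
| (b) g = 20% | 16.8% vs 11.2% | 0.667 | 87.5% |
| (c) Planning rates are OR rates and AND removes a share f of cases, p(1−f), f = 5% | 13.3% vs 8.87% | 0.667 | 77.7% |
| (c) f = 30% | 9.8% vs 6.53% | 0.667 | 63.2% |

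In (a) the OR wording costs power. In (b) it adds power. In (c) the AND wording costs power. The documents do not choose between them: section 4.2 does not say which instrument produced its 14%.

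**The case against.** The strongest reply is that the documents already direct floor assessors to the right algorithm. Section 7.3 requires the CAM on the floor, Section C refers delirium assessment to Supplemental remarks 2 to 4, and the CAM sheet has its own diagnosis line with the AND rule. Assessors are trained on both instruments by a psychiatrist. A natural workflow is to reach the diagnosis on the CAM sheet and copy it to the grid, and the CAM sheet would then allow a floor diagnosis to be recovered. Most of this stands. It narrows the defect to a wrong heading and a missing rule of precedence. It does not remove it: no section tells the assessor to copy the CAM result across, and an assessor who did so could leave a grid whose ticked features contradict its diagnosis.

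A reader might infer that the CRF applies the CAM-ICU rule to floor patients. The grid does not go that far. It prints a heading and no combining rule. The table also survives only partly in the available text, so the absence of a field for the instrument used is likely but not certain.

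A reader might also infer that the OR wording adds false positives, pulls the relative risk towards 1 and costs power. That presumes that patients with one limb are not delirious. The protocol itself accepts one limb as sufficient in PACU and ICU, and scenarios (b) and (c) lead elsewhere. Such patients may also be few. The outcome is any positive finding over up to ten assessments, so a patient's final status differs only if no assessment is positive under the CAM.

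The grid also numbers Features 3 and 4 in the reverse of the CAM order. Both instruments accept either one, so this changes no diagnosis and is not part of the point.

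**Conclusion.** The contradiction holds. For the same floor patient, two printed forms can give opposite results on the primary outcome, always positive under the grid heading and negative on the CAM sheet, and no section says which one counts. This rests on the legible wording of the forms and on one inference, that the grid's features are combined by the rule common to both instruments.

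The size is unknown. The documents give neither the frequency of one-limb patients nor the instrument behind the 14%, so no direction of effect on power can be claimed; the calculated values, from 63.2% to 87.5%, only illustrate that it can go either way. Under 5.2 the postoperative assessors are blinded to allocation, so no bias between arms is shown. The matter is an ambiguous case definition that should be corrected, and floor diagnoses can be derived from the CAM sheets that 7.3 calls for.

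**What to change.** 1. On the CRF delirium grid, record the instrument (CAM or CAM-ICU) at each assessment and print that instrument's Feature 1: the Supplemental remark 3 wording for floor assessments, the Supplemental remark 4 wording for PACU and ICU.
2. Add to 8.1 and 13.5 that postoperative delirium is derived from the item responses, using the algorithm of the instrument that 7.3 assigns to the patient's location at that assessment.
3. For forms already completed, derive floor diagnoses from the Supplemental remark 3 sheets before allocation is unmasked.

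The cost is a CRF revision and a short derivation rule. No extra assessments are needed. The observed incidence may be slightly lower than under the OR wording.

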**Record of adverse events**

An adverse event indicates any unpredictable, unfavorable medical event that is associated with any medical intervention and occurs during the study period. It can be related to the study or not.

A severe adverse event indicates any unpredictable medical events that lead to death, threat to life, prolonged length of stay in hospital, persistent disability or dysfunction, or other severe results.

Any adverse event should be followed up until it is completely resolved or therapy terminated.

**Is there any new adverse event within 24 hours after surgery:** Yes; No

**Is there any new severe adverse event within 3 days after surgery:** Yes; No

(Report form of severe adverse event see attached table)

	Start time	End time	Diagnostic evidence	Mode of occurrence	Is it severe adverse event?	Treatment 	Outcome 	Related to study?
Recall 				 Persistent  Transient	 Yes  No			 Yes  No
Hypotension 				 Persistent  Transient	 Yes  No			 Yes  No
Bradycardia 				 Persistent  Transient	 Yes  No			 Yes  No
Hypertension 				 Persistent  Transient	 Yes  No			 Yes  No
Tachycardia 				 Persistent  Transient	 Yes  No			 Yes  No
Hypoxemia 				 Persistent  Transient	 Yes  No			 Yes  No
Other:				 Persistent  Transient	 Yes  No			 Yes  No
Other:				 Persistent  Transient	 Yes  No			 Yes  No
Other:				 Persistent  Transient	 Yes  No			 Yes  No

Treatment refers to any intervention that intends to reverse or treat the adverse event;

Outcomes include: A=Recovered, B=Deteriorated, C=Persist, D=Recovered but with sequelae, E=Fatal, F=No follow-up (reasons must be explained);

Recall means the patient can recall the surroundings or an event related to the surgery while under general anesthesia.

Defined as SBP< 90 mmHg or a decrease of more than 20% from the baseline value;

Defined as HR< 50 bpm or a decrease of more than 20% from the baseline value;

Defined as SBP> 160 mmHg or an increase of more than 20% from baseline;

Defined as HR > 100 bpm or an increase of more than 20% from baseline;

Defined as SpO2< 90%.

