### **6.5 Anesthesia protocol for both intervention and control group**

- 1) During the study period (from preop to postop day 5), anticholinergics such as scopolamine are strictly prohibited; atropine or glycopyrrolate can only be used for treatment of bradycardia; the use of midazolam for anxiolysis is allowed but not encouraged;
- 2) In both arms, the anesthesia induction is per standard care using agents of lidocaine, propofol, sufentanyl and muscle relaxant. The administration of propofol in the intervention arm is via pump infusion and guided by SedLine.
- 3) The anesthesia is maintained using propofol infusion (0-200 mcg/kg/min) and remifentanyl infusion (0.05-0.2 mcg/min/kg). Sufentanyl and muscle relaxant boluses can be used during surgery.
- 4) The anesthetic adjustment in the control arm is per the conventional practice (EEG monitored but blinded to anesthesia team) and in the intervention arm per the **Supplemental remark 1. SedLine-Guided Intervention Flow Chart**.

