## 7.2 Intraoperative data

- 1) Surgical details including type and time of surgery;
- 2) Anesthetic details including the name and dose of any drugs used during surgery;
- 3) The total dose of propofol used for anesthesia induction and maintenance;
- 4) Inputs and outputs including the name and volume of the fluid being administered, the estimated blood loss, the urine output, and any blood products being transfused;
- 5) EEG data including the occurrence, duration and percentage of burst-suppression, SEF and PSI (specific to SedLine monitor).

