## 9. Adverse events

### 9.1 Definition

- 1) An adverse event indicates any unpredictable, unfavorable medical event that is associated with any medical intervention and occurs during the study period. It can be related to the study protocol or otherwise. It can manifest as any uncomfortable signs (including abnormal laboratory findings), symptoms or transient morbidity;
- 2) Predicted adverse events in this study:
  - Tachycardia: heart rate > 100 beats per minute or, in case of a baseline value > 83 beats per minute, an increase of more than 20% from baseline;
  - Hypertension: systolic blood pressure > 160 mmHg or, in case of a baseline value > 133 mmHg, an increase of more than 20% from baseline;
  - Bradycardia: heart rate < 55 beats per minute or, in case of a baseline value < 69 beats per minute, a decrease of more than 20% from baseline (before study drug infusion);
  - Hypotension: systolic blood pressure < 95 mmHg or, in case of a baseline value < 119 mmHg, a decrease of more than 20% from baseline;

- Recall: the patient remembers the details of the event(s) that occurs during the period when the patient is under appropriate general anesthesia per standard of care.

Note: for heart rate and blood pressure, the average values measured before surgery are used as baseline values.

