## Flow chart of the study

	Screen	Recruitment	Intraoperative	Postoperative follow-up								
				PACU	D1	D2	D3	D4	D5	D6-discharge	D30±3	
Inclusion/exclusion criteria	X	X										
Informed consent	X											
Demographic data	X	X										
Preoperative diagnosis	X	X										
Previous medical history	X	X										
Physical examination	X	X										
Auxiliary examination	X	X										
MMSE	X	X										
Baseline CAM	X	X										
Anesthesia			X									
Study protocol execution		X	X	X	X	X	X	X	X	X	X	X
Delirium assessment*				X	X	X	X	X	X			
Adverse events				X	X	X	X	X	X	X		
NRS of severity of pain				X	X							
NRS of subjective sleep quality					X							
Use of other drugs				X	X	X	X	X	X	X		
Postoperative complications**				X	X	X	X	X	X	X		X
All-cause 30-day mortality												X

\*Delirium will be assessed at PACU and twice daily (8:00-10:00 am and 18:00-20:00 pm) during postoperative day 1 to 5.

\*\*Patients will be followed up until postoperative day 30.

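### Section 9 requires adverse events to be documented throughout the study period, but the schedule and CRF prompts cover only the time after surgery, so haemodynamic events during the EEG-guided anaesthetic are unprompted

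*Combined protocol and SAP*

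**What the plan says.** **Protocol text (wide).** Section 9.1 defines an adverse event as one that "occurs during the study period". Section 6.5, item 1, gives the span: "During the study period (from preop to postop day 5". Section 9.1 lists tachycardia, hypertension, bradycardia, hypotension and recall as predicted events and takes pre-surgery heart rate and blood pressure as baseline. Section 9.2 includes changing the anaesthetic among the responses to each of the four haemodynamic events. Section 9.3 requires every adverse event to be documented with its timing and duration.

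**Collection tools (narrow).**
- In the Flow chart of the study, the "Adverse events" row is marked at PACU, D1 to D5 and D6-discharge. The Intraoperative cell is blank.
- The CRF page Record of adverse events opens with "Is there any new adverse event within 24 hours after surgery" and "Is there any new severe adverse event within 3 days after surgery".
- Section 7.3 places adverse events among the postoperative data: "If an adverse event occurs during patient hospitalization, it will be followed up until its disappearance or therapy ends".
- Section 7.2 lists surgical details, drugs and doses, propofol totals, fluids and, last, "EEG data including the occurrence, duration and percentage of burst-suppression, SEF and PSI". It has no heart-rate, blood-pressure or adverse-event item, and neither do the intraoperative CRF pages available here.

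**The concern.** The randomised difference in care is how the anaesthetic is given. Under Sections 6.4 and 6.5 the intervention arm has propofol titrated to the EEG from induction through surgery, while the control arm has conventional practice with the screen covered. The documents describe no difference in care afterwards. Events with onset in PACU or later can therefore show at most a carry-over effect.

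If staff follow the schedule and answer the CRF questions as worded, nobody is asked about blood pressure or heart rate during the one period in which the intervention could change them. Whether such an event reaches the form then depends on individual initiative. The people present who know the allocation are the anaesthesiologist and the study coordinator (Section 5.2). The blinded postoperative assessors did not see the anaesthetic. What is at stake is the account of intraoperative safety, not the delirium result.

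**Working it through.** No calculation drives this point; it rests on comparing passages.

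**1. The plan's own figure.** The only power figure is in Section 4.2. With p1 = 0.14, p2 = 0.14 × 2/3 = 0.0933 and mean 0.1167:

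n = [1.96 √(2 × 0.1167 × 0.8833) + 0.842 √(0.14 × 0.86 + 0.0933 × 0.9067)]² / (0.0467)² = 742 per group.

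This agrees with the plan, concerns delirium only, and is unaffected by the point.

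**2. Does the study period include the anaesthetic?** Yes. It runs from before surgery to postoperative day 5 (6.5). Section 9.2 also presupposes events under anaesthesia, because changing the anaesthetic is one of the listed responses.

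**3. What is scheduled?** Marks in the adverse-event row: PACU (1) + D1 to D5 (5) + D6-discharge (1) = 7, of which 0 are intraoperative. In the same table the Anesthesia row has its mark under Intraoperative, so the blank cell does not look like a column shift on that side of the table.

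**4. What does the CRF ask?** Both lead questions count from surgery onwards (24 hours; 3 days for severe events). Neither reaches back to induction.

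**5. Is there another intraoperative field?** None for heart rate, blood pressure or adverse events in Section 7.2 or on the intraoperative CRF pages available here.

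**6. Which predicted events are affected?** Four of the five in Section 9.1. Recall arises under anaesthesia but can only be elicited afterwards, so a postoperative question can still find it.

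**7. Is there one definition to record against?** No. Section 9.1 applies its 20% rule only at certain baselines; the CRF footnotes apply it at any baseline. The fixed cut-offs also differ for hypotension (95 against 90 mmHg) and bradycardia (55 against 50 bpm). Using baselines that appear in Section 9.1:

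| Event | Baseline | Event under 9.1 | Event under CRF footnotes |
|---|---|---|---|
| Hypotension | 133 mmHg | below 95 | below 0.8 × 133 = 106.4 |
| Hypertension | 119 mmHg | above 160 | above 1.2 × 119 = 142.8 |
| Bradycardia | 83 bpm | below 55 | below 0.8 × 83 = 66.4 |
| Tachycardia | 69 bpm | above 100 | above 1.2 × 69 = 82.8 |

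Prompting alone would therefore not give a single consistent variable.

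**The case against.** The strongest reply is that the protocol already requires what is asked for, and much of it stands.

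- A reader might infer that adverse-event collection begins only after surgery. The documents do not support that. Section 9.3 covers any adverse event, and the CRF page repeats the study-period definition and has named rows for the four haemodynamic events with start and end times. An intraoperative event can be entered. Severe events also have their own 24-hour reporting route in Section 10.3.
- A reader might infer that the arms cannot be compared at all on intraoperative haemodynamics. That goes too far. Section 7.2, item 2, records the name and dose of every drug given during surgery, and Section 9.2 names the treatments, so drug-treated events have a partial proxy. Untreated events, and those managed by fluid or anaesthetic adjustment alone, are not identified this way.
- A reader might infer a bias towards no difference. The direction cannot be derived. Unprompted entries by staff who know the allocation could err either way.
- No haemodynamic event is a listed outcome, Section 13 plans no comparison of adverse events between arms, and the Section G table shell contains none of the four. No planned test is therefore damaged. The documents also give no intraoperative event rate, so no power figure can be attached.

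What remains is that a general duty to document is not a prompt. Section 9.3 names nobody responsible for the intraoperative period, and the schedule and CRF questions point staff elsewhere.

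**Conclusion.** The point holds as an inconsistency between Section 9 and the tools meant to carry it out. Capture of four of the five predicted events is unscheduled and unprompted from induction to PACU, which is the whole period in which the arms are treated differently. Recording is likely to be incomplete and may differ by arm, so the trial could not reliably describe the intraoperative safety of EEG-guided care. The number of events that would be missed cannot be estimated from the documents.

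The primary outcome, the sample size and the listed secondary outcomes are unaffected. This should be fixed, but the delirium analysis does not depend on it.

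The verdict assumes that the study period stated in Section 6.5 also applies in Section 9.1, and that no other intraoperative adverse-event form exists. Absence is asserted only for the pages available; the flow chart in Supplemental remark 1 is not reproduced in the text.

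**What to change.** 1. In the Flow chart of the study, mark the adverse-event row under Intraoperative.
2. Add intraoperative adverse events to Section 7.2.
3. On the CRF page, start the adverse-event question at anaesthesia induction. Record each predicted haemodynamic event separately for induction to PACU arrival and for after PACU arrival.
4. State in Section 13 that both periods will be reported by arm. Descriptive reporting is enough.
5. Take intraoperative values from the anaesthesia record by a fixed rule, because the person recording in the operating room knows the allocation. This assumes the record holds serial heart rate and blood pressure, which the documents do not describe.
6. Reconcile Section 9.1 with the CRF footnotes so that one definition of each event applies in both periods. Which definition is for the sponsor to decide.

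**Cost.** The document changes are small, and the coordinator already collects data in the operating room. The real cost is abstracting the anaesthesia record for each patient, up to 2 × 780 = 1,560. No clinical rule, outcome or sample size changes.
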